6.5.4 Events involving lower limb amputation

This definition includes amputation (i.e. resection of a limb through a bone), disarticulation (i.e. resection of a limb through a joint) and auto-amputations (i.e. spontaneous separation of non-viable portion of the lower limb).

Not included in this definition are debridement (removal of callus or dead tissue), procedures on a stump (like stump revision, drainage of an abscess, wound revision etc.) and other procedures (e.g., nail resection or removal) without a concomitant resection of a limb (amputation or disarticulation).

Each lower limb amputation, disarticulation, or auto-amputation should be reported separately. The SAE report should include the date of the procedure, the level of amputation or disarticulation, the medical condition(s) leading to the procedure and if the patient had some of the known risk factor(s) for lower limb amputation.

6.6 Serious Adverse Events (SAE)

An SAE is defined as any event that

- Results in death;
- Is immediately life-threatening*;
- Requires hospitalisation or prolongation of existing inpatient's hospitalisation**
- Results in persistent or significant disability or incapacity;
- Is a congenital abnormality or birth defect;

* "Life-threatening" in the definition of "serious" refers to an event in which the subject was at risk of death at the time of the event; it does not refer to an event which hypothetically might have caused death if it were more severe.

** "Hospitalisation" means any unexpected admission to a hospital department. It does not usually apply to scheduled admissions that were planned before study inclusion or visits to casualty (without admission).

Medical judgement should be exercised in deciding whether an adverse event/reaction is serious in other situations. Important adverse events/reactions that are not immediately life-threatening, or do not result in death or hospitalisation but may jeopardise a subject, or may require intervention to prevent one of the other outcomes listed in the definition above should also be considered serious.

Patients may be hospitalised for administrative or social reasons during the study (e.g. days on which infusion takes place, long distance from home to site,). These and other hospitalisations planned at the beginning of the study do not need to be reported as a SAE in case they have been reported at screening visit in the source data and have been performed as planned.

Worsening of the underlying disease or other pre-existing conditions

Worsening of the underlying disease or of other pre-existing conditions will be recorded as an (S)AE in the (e)CRF.

Changes in vital signs, ECG, physical examination, and laboratory test results

Changes in vital signs, ECG, physical examination and laboratory test results will be recorded as an (S)AE in the (e)CRF, if they are judged clinically relevant by the investigator.

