2.3 Primary outcome

Difference in number of sVT/VF episodes between treatment groups from randomization to week 52

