6. ADVERSE EVENTS (AE)

An AE is any untoward medical occurrence in a patient or clinical trial subject administered a medicinal product and which does not necessarily have a causal relationship with this treatment. An AE can therefore be any unfavourable and unintended sign (including an abnormal laboratory finding), symptom, including an exacerbation of a pre-existing condition, or disease temporally associated with the use of the trial device/procedure, whether or not considered related to the treatment.

All adverse events that occur during this study will be recorded on the adverse event case report forms.

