6.5 Adverse events of Special Interest (AESIs)

The term AESI relates to any specific AE that has been identified at the project level as being of particular concern for prospective safety monitoring and safety assessment within this trial, e.g. the potential for AEs based on knowledge from other compounds in the same class. AESIs need to be reported to the Pharmacovigilance Department of MSD within the same timeframe that applies to SAEs.

Patients with AESIs need to be followed up appropriately, regardless of the origin of the laboratory data (e.g. central, local etc.). The Investigator should consider which, if any, concomitant therapies should not be taken during evaluation. Discontinued treatments can be reintroduced per Investigator discretion.

The following are considered as AESIs:

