##### **2.2.3 Safety endpoints**

- All-cause mortality
- Number of serious adverse events
- Number of hypoglycaemic events
- Number of genital infections
- Number of ketoacidotic events
- Changes in liver function parameters (AST, ALT, GGT)

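### The SAE endpoint is one total that includes efficacy-type events, so a treatment benefit would dilute any rise in other SAEs

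*Protocol*

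**What the plan says.** Protocol 6 defines an adverse event broadly, "including an exacerbation of a pre-existing condition". Protocol 6.6 makes an event serious if, among other criteria, it "Results in death", "Is immediately life-threatening" or "Requires hospitalisation or prolongation of existing inpatient's hospitalisation". On disease progression it adds: "Worsening of the underlying disease or of other pre-existing conditions will be recorded as an (S)AE in the (e)CRF". The only carve-outs are hospital stays that were planned beforehand or are administrative or social. Nothing exempts an event because it is also a trial endpoint.

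The same kinds of event are efficacy outcomes. The primary outcome in Protocol 2.3 is "Difference in number of sVT/VF episodes between treatment groups from randomization to week 52". Heart-failure admissions and cardiovascular mortality are secondary outcomes in Protocol 2.4 and SAP 2.2.2.

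On the safety side, SAP 2.2.3 lists "Number of serious adverse events", and Protocol 2.2 has the same item. SAP 5 gives methods for the primary and secondary endpoints but none for safety endpoints. SAP 6 describes generic summaries by arm. Protocol 6.3 has investigators record causality, but no analysis of it is specified. Protocol 6.5 describes AESIs as "being of particular concern for prospective safety monitoring and safety assessment within this trial", yet neither document specifies an AESI table by arm.

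**The concern.** A total SAE count is usually read as a summary of harm. Here part of that total consists of events the drug is expected to prevent. If the hypothesis is true, that part falls on ertugliflozin and a rise in the remaining SAEs is diluted or, in some configurations, offset. A reader could then take a ratio near 1 as reassurance about other serious harms when it is the sum of a benefit and a harm.

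The endpoint is also a count of events, not of patients. Protocol 7 treats sVT/VF as recurrent and over-dispersed, so a few patients with repeated serious episodes could dominate the total.

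**Working it through.** The documents state no SAE rate, SAE share or SAE comparison, so there is no plan figure to reproduce. The check is how far a benefit on one part of the total can offset an excess in the rest.

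**Inputs**
- RR_E, the rate ratio for efficacy-type SAEs: 0.70, the 30% reduction planned for sVT/VF in Protocol 7.1 and SAP 4. Applying it to heart-failure admissions and cardiovascular deaths as well is an assumption; 0.80 is shown as an alternative.
- f, the share of placebo-arm SAEs that are efficacy-type: not in the documents; 0.2 to 0.6 assumed.
- RR_O, the rate ratio for all other SAEs: the unknown of interest.

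**Formulas**
- RR_total = f × RR_E + (1 − f) × RR_O
- Setting RR_total = 1 gives the break-even RR_O = (1 − f × RR_E) / (1 − f)

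For f = 0.2 and RR_E = 0.70: (1 − 0.14) / 0.8 = 1.075. For f = 0.6: (1 − 0.42) / 0.4 = 1.45.

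| f | Break-even RR_O, RR_E 0.70 | Break-even RR_O, RR_E 0.80 | RR_total if RR_O = 1.30, RR_E 0.70 |
|---|---|---|---|
| 0.2 | 1.075 | 1.05 | 1.18 |
| 0.3 | 1.129 | 1.086 | 1.12 |
| 0.4 | 1.20 | 1.133 | 1.06 |
| 0.5 | 1.30 | 1.20 | 1.00 |
| 0.6 | 1.45 | 1.30 | 0.94 |

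**In counts.** Take 191 per arm, 0.95 year (11.4 months), an assumed 0.6 SAEs per patient-year on placebo, f = 0.5 and a true 30% excess of other SAEs.
- Placebo: 191 × 0.95 × 0.6 = 108.9 SAEs, of which 54.4 are efficacy-type and 54.4 other.
- Ertugliflozin: 54.4 × 0.70 = 38.1 efficacy-type and 54.4 × 1.30 = 70.8 other, total 108.9.
- The pooled count shows no difference. The count without efficacy-type events shows a ratio of 1.30.

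**Using the plan's sVT/VF rates.** Let s be the share of sVT/VF episodes that qualify as SAEs and r0 the control rate, which is 1.3 per year in SAP 4 and 1.0 in Protocol 7.1. Assume 0.4 other SAEs per patient-year on placebo and a true 50% excess (0.6 on drug). Then RR_total = (0.70 × s × r0 + 0.6) / (s × r0 + 0.4).

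| s | r0 = 1.3 | r0 = 1.0 |
|---|---|---|
| 25% | 0.8275 / 0.725 = 1.14 | 0.775 / 0.65 = 1.19 |
| 50% | 1.055 / 1.05 = 1.00 | 0.95 / 0.90 = 1.06 |
| 100% | 1.51 / 1.70 = 0.89 | 1.30 / 1.40 = 0.93 |

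This second version leaves out heart-failure admissions and cardiovascular deaths. In every cell the total understates the true ratio of 1.50. Whether it is merely diluted or falls to 1 or below depends on s and r0. Arm size and follow-up cancel from these ratios, so early termination (SAP 7) does not change the dilution, but it leaves fewer events with which to see a difference.

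**Coverage of AESIs.** Protocol 6.5 against the safety lists in Protocol 2.2 and SAP 2.2.3:
- Hepatic injury: AST, ALT and GGT changes are listed; the threshold events are not.
- Decreased renal function: creatinine and eGFR changes are listed; the doubling event is not.
- Acidosis and ketoacidosis: ketoacidotic events are listed.
- Lower-limb amputation: not listed in any form.

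Scheduled bloods are drawn only at baseline and week 52 (Protocol 5.5.5), so a liver or renal event that resolves mid-year may not show in the listed changes.

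**The case against.** Several counter-arguments carry weight.

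- Recording disease worsening is a normal reporting rule, and (S)AE means adverse event or SAE, so the sentence does not by itself make worsening serious. This stands. The rule is not the defect; the overlap arises through the seriousness criteria, and the gap is in the summary.
- Not every sVT/VF episode is an SAE. Protocol 6.6 limits life-threatening to actual risk of death at the time and leaves other cases to medical judgement. This stands, and it is why the efficacy-type share is unknown.
- Total SAEs are a legitimate measure of net harm. Demoting them would take any arrhythmic or heart-failure harm out of the main safety figure, although Protocol 2.2 lists electric storm as a safety objective. This stands, so the total should stay.
- Hypoglycaemia, genital infections, ketoacidosis, liver and renal parameters and all-cause mortality are separate endpoints. This stands in part: it limits the exposure, but it does not cover serious events outside those lists.

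A reader might infer that the SAP formally tests the SAE totals and would declare no excess. It does not: SAP 2.2.3 only names the endpoint, and no SAE test or ratio is specified. A reader might also infer that AESI harms go uncompared altogether. The coverage list above shows otherwise, with amputation the one complete omission.

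**Conclusion.** The concern holds as a moderate gap in the safety summary. The single SAE total includes events also analysed as efficacy outcomes, and neither document plans a version without them. At the planned rate ratio of 0.70, an excess of 7.5% to 45% in other SAEs would be fully offset when efficacy-type events make up 20% to 60% of placebo SAEs; at 0.80 the range is 5% to 30%. These figures rest on an assumed share and on one rate ratio applied to all efficacy-type events. Given a real benefit on those events and a rise in other SAEs, the direction of the dilution does not depend on the share.

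It would be tempting to conclude that the trial must hide a drug-related harm. The documents do not support that. Exact cancellation needs a particular combination of benefit, share and excess; in other combinations the excess is diluted but still visible, or the total falls below 1.

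**What to change.** In SAP 2.2.3 and 5:
- Keep total SAEs. Beside them report, by arm, SAEs other than sVT/VF, heart-failure hospitalisation and cardiovascular death, as patients with at least one event and as events per patient-year.
- Identify the overlap before unblinding by matching SAEs to the recorded endpoint events. State how events between week 52 and the telephone visit are classed: Protocol 2.4 runs heart-failure admissions and cardiovascular mortality to week 56, SAP 2.2.2 only to week 52.
- Tabulate AESIs by arm, including amputations.

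Recording and expedited reporting of SAEs stay as they are. The cost is one or two extra tables from data already collected and a blinded matching step, with no new assessor needed.

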6.6.1 Reporting of SAEs

The study sites shall report (i.e., from signing the informed consent onwards through the trial defined follow-up period) all SAEs and non-serious AEs which are relevant for a reported SAE and Adverse Events of Special Interest (AESI) by fax or other secure method using the FDA Safety Information Form to the MSD Unique Entry Point immediately (within twenty four (24) hours or next business day whichever is shorter)

Merck Sharp & Dohme Ges.m.b.H

The ICON Vienna

[name]

[contact]

The sponsor will report the SAE to the ethics committee and the local authorities.

A suspected unexpected serious adverse reaction (SUSAR) is designated as such according to Guideline 2001/20/EG.

A serious adverse reaction is deemed unexpected when it is not listed in the corresponding basic document (Summary of Product Characteristics, IB, IMPD).

7. STATISTICAL ANALYSES

The sample size calculations and the primary statistical method are based on the primary endpoint, which is the number of VT/VF episodes from randomization to week 52. The primary objective is to compare the rate of VT/VF episodes across the two experimental arms. The number of VT/VF episodes within 52 weeks can be considered as a discrete variable with relatively few possible values (0, 1, 2, 3 ...) per patient. This fact prevent us from using the most common statistical methods in clinical trials that assume normality, such as Student's t-test, linear regression or

analysis of variance. We, instead, will use the negative binomial regression model, which is most appropriate in the case of recurrent events (the current situation), allows investigation of the treatment effect and confounding variables, and adjusts for variable follow-up times by using time at risk as the offset. For more details on the arguments to use the negative binomial models in this kind of research, please see: (18). Furthermore, the negative binomial will be used instead of the Poisson distribution (also used for modelling count data) due to expected over-dispersion in the data.

7.1 Sample size and power considerations

Previous data showed that VT/VF episodes are decrease by two thirds within 6 months after initiation of sacubitril/valsartan in ICD±CRT patients (10). sVT/VF Episodes declined by 62.5% whereas nsVTs rate dropped by ~70%. Based on comparable effects on heart failure morbidity with either SGLT-2 inhibition or sacubitril/valsartan treatment we expect a profound reduction in sVT/VF in the treatment arm. Since data of the large SGLT2 outcome trials which did not focus on arrhythmias and their detection but only counted cases of sudden cardiac death have a signal of smaller effects we calculate with a decrease in the event rate of 30%. Moreover, the retrospective analysis by Martens et al provides a rather low event rate in their population. However, as pointed out in the Introduction other prospective randomized trials have considerably higher event rates. The sample size calculation is based on the mathematical formula provided by Zhu and Lakkis for comparing event rates of two negative binomial distributions (19). We used the function power.nb.test of the package MKmisc in R that implements the results of the paper cited above. According to that formula, the parameters needed to calculate the sample size are: The expected yearly rate of VT/VF episodes in the control group (r_0), The minimal clinical relevant effect (RR) defined here as the ratio of expected VT/VF episodes rates (RR = expected rate in treated/expected rate in control = r_1/r_0), the average follow-up or treatment duration (duration), the negative binomial dispersion parameter (k), the Type I error probability (α) and the power ($1 - \beta$). To detect a 30% reduction in VT/VF episodes rate in the ertugliflozin group as compared to the placebo group (i.e. using RR = 0.70), with a power of 80% and an alpha-level of 0.05%, a sample size of 191 patients in each group is needed. In this sample size calculation, we assumed the dispersion parameter k to be 1.0, the expected yearly rate of VT/VF episodes in the control group (i.e. r_0) to be 1.0 and an average follow-up of 11.4 months. To account for a dropout rate of about 5% in each group, we will need of 402 patients in each arm.

Out of the > 1000 patients with ICD±CRT being seen at our out-patients clinic >50% have experienced episodes of non-sustained VT within the last 12 months. In order to enrich the study population with higher risk patients at least one additional inclusion criterion has to be met (either nt-proBNP > 500pg/mL or LV-EF < 35% or hospitalization for heart failure within the last 12 months or >100nsVTs or >1sVT/VF episode within the last 12 months).

About 5-10% of our patients are currently treated with ARNI. Expecting similar numbers in the other participating centers we feel confident to recruit patients for this trial within 18 months. Moreover, the recent DAPA-HF trial with 11% of patients on ARNI therapy revealed an unaltered benefit of SGLT-2 inhibition in these patients(2).

Taking into account that compared to the Martens-trial the expected reduction in the applied study is much lower, the observation period twice as long and the populations risk is enriched due to the inclusion criteria the calculation can be rated conservative.

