Therefore, every improvement of heart failure should result in a reduction of ventricular arrhythmias. This has been shown extensively for beta-blockers(6), aldosterone-antagonists(7; 8), and ARNIs(9; 10). Large outcome studies with ACE inhibitors did only give limited insight in the type of arrhythmic events, their causes, and the effect of the treatments(11; 12), while studies analysing the rate of ventricular arrhythmias did show a significant reduction in these events(13).

Previous data showed that SGLT-2 inhibitor dapagliflozin (DAPA-HF) improved primary outcome in a HFrEF population comparable to sacubitril/valsartan in the PARADIGM trial(9) (both trials with a NNT of 21). Therefore, a comparable impact on heart failure morbidity and ventricular arrhythmias can be assumed for both drugs. Moreover, Martens et al. reported on a highly significant reduction of ventricular arrhythmias after initiation of sacubitril/valsartan in a retrospective analysis of 151 patients with an observation period of 6 months. The number of VT/VF episodes declined by more than two thirds(10).

Mortality in patients on ICD therapy is high despite optimal medical treatment. The study by Martens is a retrospective analysis of data of patients that were followed throughout the observation period of 364 days.

Therefore, severely ill patients and at least those who died within these 12 months were not analysed. Obviously, these patients tend to have the highest burden of ventricular arrhythmias. Therefore, event rate in the Martens study is underestimated.

More reliable data on event rates derive from prospective randomized trials such as the RAFT study. They report a rate of VTs of ~2 per year (11278 appropriate ICD detections in 5953.6 patient-years of follow-up) in a cohort of patients with severely reduced left ventricular ejection fraction (<30%).

Within another increased-risk population treated in the SHIELD trial 58% of the placebo-group experienced “all-cause shocks plus symptomatic tachyarrhythmias terminated by ATP”. The overall number of episodes was 1595 in 214 patients (average of ~7.5/patient and year).

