## Ertugliflozin to Reduce Arrhythmic burden in ICD/CRT patientS (ERASE-Trial) – a phase III Study

on the mathematical formula provided by Zhu and Lakkis for comparing event rates of two negative binomial distributions (11). We used the function `power.nb.test` of the package `MKmisc` in R that implements the results of the paper cited above. According to that formula, the parameters needed to calculate the sample size are: The expected yearly rate of VT/VF episodes in the control group ( $r_0$ ), The minimal clinical relevant effect (RR) defined here as the ratio of expected VT/VF episodes rates (RR = expected rate in treated/expected rate in control =  $r_1/r_0$ ), the average follow-up or treatment duration (duration), the negative binomial dispersion parameter ( $k$ ), the Type I error probability ( $\alpha$ ) and the power ( $1 - \beta$ ). To detect a 30% reduction in VT/VF episodes rate in the ertugliflozin group as compared to the placebo group (i.e. using RR = 0.70), with a power of 80% and an alpha-level of 0.05%, a sample size of 191 patients in each group is needed. In this sample size calculation, we assumed the dispersion parameter  $k$  to be 1.0, the expected yearly rate of VT/VF episodes in the control group (i.e.  $r_0$ ) to be 1.3 and an average follow-up of 11.4 months. To account for a dropout rate of about 5% in each group, we will need of 402 patients in total.

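### The dispersion k = 1.0 behind the 80% power has no source, the one informative cited trial points well above 1, and the claim of conservatism leaves dispersion out

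*Protocol*

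**What the plan says.** Protocol section 7 chooses the negative binomial over the Poisson because over-dispersion is expected. Section 7.1 then fixes its amount: "we assumed the dispersion parameter k to be 1.0". SAP section 4 makes the same assumption. Neither document names a source for k or varies it.

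The other inputs are a rate ratio of 0.70 ("i.e. using RR = 0.70"), a control rate and follow-up given in the Protocol as "to be 1.0 and an average follow-up of 11.4 months" and in the SAP as "to be 1.3 and an average follow-up of 11.4 months", and a calculation "with a power of 80% and an alpha-level of 0.05" (printed with a percent sign, read here as 5%). Both documents arrive at 191 per group. The test is two-sided in Protocol 7.2 and in the hypotheses of SAP section 5.

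Protocol 7.1 closes by saying that "the calculation can be rated conservative". Its grounds are that, compared with the retrospective sacubitril/valsartan analysis, the assumed reduction is smaller, the observation is longer and the population is at higher risk.

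The Introduction of both documents cites two prospective ICD trials for their event rates. For the increased-risk one (SHIELD) it reports that "58% of the placebo-group experienced" an event and that "The overall number of episodes was 1595 in 214 patients", about 7.5 per patient and year.

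**The concern.** In a negative binomial comparison, the variance of the log rate ratio has one part that shrinks as events accrue and one part, set by k, that does not. The plan argues for caution on the event rate from outside trials but takes nothing from them about spread between patients. If k is well above 1, the planned size has much less power than stated, and a higher event rate helps only up to a ceiling. A non-significant result could then be read as evidence against the drug when a 30% reduction would probably have been missed.

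**Working it through.** **Inputs.** n = 191 per arm, RR = 0.70, t = 11.4/12 = 0.95 years, k = 1.0 (both documents); r0 = 1.0 (Protocol) or 1.3 (SAP); two-sided 5%. From the Introduction: mean 1595/214 = 7.453 and event-free share 1 − 0.58 = 0.42.

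**Formula.** This is the published two-rate formula that both documents cite. With true rates in the variance,

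V = (1/t)(1/r0 + 1/(0.70 r0)) + 2k = 2.556/r0 + 2k

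n = (z_α + z_β)² V / (ln 0.70)²

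power = Φ(|ln 0.70| √(n/V) − z_α), with |ln 0.70| = 0.3567.

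**The plan's own figure.** At k = 1.0 the true-rate and pooled-rate variants give:

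- r0 = 1.0: 282 and 278 two-sided, 222 and 219 one-sided.
- r0 = 1.3: 245 and 243 two-sided, 193 and 191 one-sided.

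So 191 is reproduced exactly with r0 = 1.3, a one-sided 5% test and the pooled variant. Under the stated two-sided test, 191 per arm gives 70% at r0 = 1.3 even with k = 1. That loss from 80% comes from sidedness and is a separate issue; only what is lost below 70% belongs to k.

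**What the cited figures imply for k.** For a negative binomial count with mean μ, P(0) = (1 + kμ)^(−1/k).

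- k = 1.0, μ = 7.453: P(0) = 1/8.453 = 0.12, against 0.42 cited.
- Solving for P(0) = 0.42 gives k = 3.93. Check: (1 + 29.29)^(−1/3.93) = 0.42.
- Same mean, P(0) = 0.30, 0.35, 0.50: k = 2.5, 3.0, 5.4.
- P(0) = 0.42, mean 2, 3, 5: k = 1.7, 2.4, 3.3.
- At the cited mean, k = 1.55 would need about 80% of patients with an event.

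The other prospective trial (11278 detections in 5953.6 patient-years, 1.89 per year) gives a mean only and says nothing about k.

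**Two-sided power at 191 per arm.** The last column is the 95% interval expected around 0.70 at r0 = 1.3, that is 0.70 × exp(±1.96 √(V/191)).

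| k | r0 = 1.0 | r0 = 1.3 | r0 = 7.45 | unlimited rate | interval, r0 = 1.3 |
|---|---|---|---|---|---|
| 1 | 64% | 70% | 90% | 94% | 0.53 to 0.93 |
| 2 | 49% | 52% | 66% | 69% | 0.50 to 0.99 |
| 3 | 39% | 42% | 50% | 52% | 0.47 to 1.04 |
| 3.93 | 33% | 35% | 41% | 42% | 0.45 to 1.09 |

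Example, r0 = 1.3 and k = 3.93: V = 1.966 + 7.86 = 9.826; 0.3567 × √(191/9.826) = 1.572; Φ(1.572 − 1.960) = 0.35.

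Simulated trials fitted by negative binomial maximum likelihood (400 per setting) gave 69% at (r0 1.3, k 1), 34% at (1.3, 3.93) and 38% at (7.45, 3.93), in line with the formula.

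**The ceiling.** As r0 grows, V tends to 2k. The largest k for which 191 per arm can reach 80% is 191 × 0.1272 / (2 × 7.849) = 1.55 two-sided (1.97 one-sided). At k = 1, 80% needs 2.556/r0 = 3.096 − 2, so r0 is about 2.3 per year. At k = 3.93, 80% needs about 605 per arm at r0 = 1.3, and never fewer than about 485.

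**The case against.** **The value 3.9 joins two statements that the Introduction does not join.** It does not say that the 214 patients are the placebo group, that the 1595 episodes are of the type counted in the 58%, or how follow-up varied. A broader episode count, or patients with short follow-up, would make k look too large. This stands: 3.9 is indicative, and the range above is part of the result. It does not rescue k = 1.0, since even a matching mean of 2 gives 1.7.

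**The endpoint differs.** The cited trial counted shocks of any cause plus symptomatic tachyarrhythmia ended by pacing. This trial counts sVT/VF from device records. This stands as well.

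**The relevant dispersion is residual.** SAP section 5 adjusts for the baseline sVT/VF count, and SAP 5.1 adds the stratification factors if sample size permits. That may lower k by an amount the documents do not let one estimate. The sample-size text takes no credit for it.

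**The conservatism sentence says nothing about dispersion.** Correct. A reader might infer that the sentence is simply false and should go. The documents do not support that, because its grounds are effect size, duration and enrichment. The fault is that it characterises the whole calculation while leaving out one of its main inputs.

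**The trial ended early.** SAP section 7 says the SAP was revised for early termination and a lower sample size, so power at 191 per arm describes a size that was not reached. This stands and shapes the fix. But SAP section 4 still prints 191 per group and 80%.

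**Conclusion.** The point holds in a limited form. The assumption k = 1.0 is unsupported in both documents, and the only cited data that bear on it point well above 1. Over k = 1 to 3.9, two-sided power at 191 per arm and r0 = 1.3 runs from 70% down to 35%. The stated 80%, and conservatism as a property of the whole calculation, are therefore not supported.

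This rests on negative binomial counts, on one cited trial with a different endpoint, and on its two figures being comparable. Three stronger readings are tempting and should be resisted:

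- That k in this trial is 3.9. The documents hold no dispersion data on sVT/VF.
- That 80% was out of reach at any event rate. That is so only if k exceeds about 1.55; at k = 1, about 2.3 events per year would suffice.
- That dispersion explains the whole shortfall from 80%. The first ten points come from one-sided against two-sided testing.

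**What to change.** 1. Protocol 7.1: qualify the conservatism sentence so that it refers to effect size, duration and enrichment, and state that dispersion was not considered.
2. SAP section 4: replace the single 80% figure with two-sided power over k = 1 to 4, and say that k = 1.0 is an assumption without a source.
3. Before unblinding, estimate k from the pooled counts, with and without the baseline sVT/VF count in the model. The second estimate shows the crude spread; the first is the one relevant to the planned analysis. Pooling over arms adds little: with equal arms and RR 0.70 the pooled value is (0.745/0.7225)(1 + k) − 1, so k = 1 would appear as 1.06.
4. Report the expected confidence-interval width for the rate ratio from that k at the number of patients actually enrolled, beside the figure for 191 per arm, so that a null result is read against what the trial could detect.

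The cost is a text change and one blinded estimate. No added enrolment and no change to the primary model is asked for. The downside is that the stated power becomes less favourable.
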